Medical history:	When aplastic anaemia data are contained in "180111 Medical
presence/absence of	history", it should be classified as "with aplastic anaemia. Other
aplastic anaemia	cases are "no aplastic anaemia".
Medical history:	When pancytopenia data are contained in "180111 Medical history",
presence/absence of	it should be classified as "with pancytopenia. Other cases are "no
pancytopenia	pancytopenia".
Medical history:	When malignant tumour data are contained in "180111 Medical
presence/absence of	history", it should be classified as "with malignant tumour. Other
malignant tumour	cases are "no malignant tumour".
Medical history:	When medical-history data except tuberculosis, non-tuberculous
presence/absence of	mycobacteriosis, interstitial pneumonia, bronchitis bacterial, aplastic
other medical history	anaemia, pancytopenia and malignant tumour are contained among
other medical history	the medical-history data in the survey form, it should be classified as

Data name	Derivation and calculation methods
	"with other medical history". The remaining cases are "no other
	medical history".
	When "with allergy history in "patient information" of the survey
	form is checked, it should be classified as "with allergy history.
Presence/absence of	When "allergy history unknown" is checked, it should be "unknown"
allergy history	whereas nothing is provided in "presence/absence of allergy history"
	of the form, it should be "not provided". Other cases are "no allergy
	history".
	When "Hepatitis→viral" is selected in "Complications" of "Patient
	information" in the survey form and also "B" is selected for
Patients with an hepatitis	"Hepatitis virus carrier", the patient is classified as a patient with an
B virus infection	hepatitis B virus infection. The patients also include those developed
	an adverse event encoded with the applicable MedDRA PT described
	in "patients with 180111B Hepatitis B virus infection".
	For the items for smoking history in the survey form, when the
	checkboxes of "smoking" or "in the past" are checked, or when "with
	smoking history" is checked and the smoking period is "unknown",
Presence/absence of	both cases should be classified as "with smoking history". When
smoking history	"unknown" is checked for smoking history, it should be "unknown".
	When nothing is described in "presence/absence of smoking history"
	of the survey form, it should be "not provided".
	Other cases are "no smoking history".

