	When "smoking" is checked among the items for smoking history in
	the survey form, or when any descriptions are made in the smoking
	period of "smoking", they should be classified as "smoking". When
Detailed classification of	"in the past" is checked or any descriptions are made in the smoking
	period "in the past" in patients who are not classified as "smoking",
smoking history	the case should be classified as "only in the past (not smoking now)".
	When "with smoking" is checked but nothing is checked in the
	detailed classification, or when "unknown" is checked, they should
	be "unknown".
Patients with dosing	Patients other than those who satisfied [1] to [4] of "Administration
deviation of Humira	status (dosage and administration)"
Presence/absence of	When "Self-administration" in the "Administration status of Humira"
self-administration	column is checked at least once, the case should be classified as
	"with" self-administration. Others are "without" self-administration.

Data name	Derivation and calculation methods
	When both "administration by physician" and "self-administration"
	are checked, the case should be "with self-administration".
	When "with" self-administration error is checked in the survey form,
	it should be classified as "with" the error. When "without" is
D / 1 C	checked, it should be "without" the error.
Presence/absence of	When some details are provided along with the onset date in the
self-administration error	self-administration error column irrespective of a check on
	"with"/"without", it should be regarded as "with" the error.
	If nothing is described there, it should be "unknown/not provided".
	It should be identified based on the sex in the patient's information of
G.	the survey form. When multiple items are checked or data without a
Sex	description are included, the case should be classified as
	"unknown/not provided".
	It should be identified based on pregnancy/nursing in the patient's
	information of the survey form. When multiple items are checked or
D / ·	data without a description are included even if the sex has been
Pregnancy/nursing	selected as "woman", the case should be classified as "unknown/not
	provided". If the sex is not "woman" even though a description has
	been made for this item, it is excluded from the calculation.
	It should be identified based on the race in the registration form.
Race	When multiple items are checked or data without a description are

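### As written, the SAP's smoking-history rule sends a form with 'with smoking history' ticked and a period written, but no sub-box ticked, to 'no smoking history', while the next row classes it as a smoker

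*SAP*

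**What the plan says.** SAP 10.1 General derives two linked variables from the smoking items of the survey form.

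**Presence/absence of smoking history.** There are two routes to a positive class. One is a tick in a sub-box and the other is a positive answer combined with an unknown period: "checkboxes of 'smoking' or 'in the past' are checked, or when 'with" continuing "smoking history' is checked and the smoking period is 'unknown". The row then closes the list: "both cases should be classified as 'with smoking history'. When". The 'unknown' class needs its own tick ("unknown' is checked for smoking history, it should be 'unknown"). The 'not provided' class needs an empty item ("When nothing is described in 'presence/absence of smoking history"). Everything left over is negative: "Other cases are 'no smoking history".

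**Detailed classification of smoking history.** Here a tick is not required. The class 'smoking' applies if the box is ticked in "the survey form, or when any descriptions are made in the smoking" period for current smoking. An entry in the past period works the same way for 'only in the past'. The row also provides for a positive answer without any detail: "When 'with smoking' is checked but nothing is checked in the" detailed item, the class is 'unknown'.

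Both variables are summarised in Table 1.12 and listed as background factors in Tables 2.9 and 3.4. Table 3.4.1 takes its factor list from 3.4. SAP 9.5 leaves unknown/not provided out of the tests; the 'no' class stays in.

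**The concern.** The first row ignores a smoking period that has actually been written down, whereas the second row relies on it. A positive answer with a stated period can therefore be coded negative, while the same answer with the period marked unknown is coded positive. The better documented form gets the wrong class.

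The SAP handles comparable items differently. In the same section a ticked positive allergy history is sufficient, details of a self-administration error count whatever box is ticked, and a hepatitis B test result counts as a test done even if that box is empty. In those rows a positive tick or recorded data settles the class. Here both together can still end in a residual 'no'.

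Factors that may affect safety and effectiveness are a stated objective (Protocol section 1, SAP 4.1). At stake are the agreement of the two smoking rows in Table 1.12 and the composition of the non-smoker group in the factor tests. A misplaced patient would be tested in the wrong group and not set aside as unknown.

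**Working it through.** The plan states no figure for this rule, so there is none to reproduce. The check applies both rows, as written, to every form on which the positive answer is ticked and neither sub-box is ticked.

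| Period entry | Presence/absence row | Detailed row |
|---|---|---|
| Marked 'unknown' | with | unknown |
| Written under 'smoking' | **no** | smoking |
| Written under 'in the past' | **no** | only in the past |
| Blank | **no**, unless blank is read as 'unknown' | unknown |

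For the third line the steps are:

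1. No sub-box is ticked, so the first route fails.
2. The period is known, so the second route fails.
3. The 'unknown' box is not ticked, so that class does not apply.
4. The presence/absence item has been answered, so 'not provided' does not apply.
5. Only the residual 'no' is left. The detailed row reads the written period and gives 'only in the past'.

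The second line runs the same way. These two lines are direct contradictions. The fourth depends on how a blank period is read, and its detailed class is 'unknown', so that patient is not counted as both smoker and non-smoker.

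**Size, by illustration only.** The documents give neither the share of smokers nor the share of forms with this pattern. Assume the target of 1500 patients, 30% with a smoking history (1500 × 0.30 = 450, leaving 1050), and a share *m* of those 450 forms with the pattern. Ignore unknown/not provided. Then:

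- misplaced = 450 × *m*
- share of the 'no' group = misplaced / (1050 + misplaced)
- observed difference = true difference × (1 − that share), if misplaced patients have the smokers' rate

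With assumed adverse-reaction rates of 30% in smokers and 20% in non-smokers (a true difference of 10 points):

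| *m* | Misplaced | Share of 'no' group | Observed difference |
|---|---|---|---|
| 2% | 9 | 9/1059 = 0.8% | 9.9 points |
| 5% | 22.5 (about 23) | 22.5/1072.5 = 2.1% | 9.8 points |
| 10% | 45 | 45/1095 = 4.1% | 9.6 points |

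A wider range gives, at one end, 20% smokers and *m* = 5%: 15/1215 = 1.2%, so 9.9 points. At the other end, 40% smokers and *m* = 20%: 120/1020 = 11.8%, so 8.8 points.

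**The case against.** The strongest reply is that no affected patient is shown. The survey form is not among the documents. It may offer exactly three options under a positive answer (current, past, period unknown), in which case the first row lists them all and only an incompletely ticked form escapes. Protocol section 6(3) has the medical representative check and recheck the forms, and section 12 includes reinvestigation, so many gaps may have been closed before lock. The apparent intent is also clear: the detailed row treats a ticked positive answer as belonging to a smoker, so programmers may have coded every such tick as positive. Finally, smoking history and its detail are 2 of 57 factors screened one at a time, and they define no endpoint or analysis set.

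Most of this stands as a limit on size. A reader might infer that recorded smokers were in fact analysed as non-smokers, or that the smoking comparisons are materially distorted. The documents support neither: they show a rule that would misclassify a certain form, not that such forms exist, and the dilution under plausible assumptions is small.

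The reply does not remove the conflict. The detailed row provides for a missing sub-box tick and for a period written without one, so the authors foresaw such forms. They are collected on paper (Protocol section 6(3)), where partial ticking is plausible. Intent that has to be guessed from a neighbouring row is not a specification.

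**Conclusion.** The point holds as a minor error of specification. For a positive answer with a written period and no sub-box tick, the presence/absence row gives the wrong class and contradicts the detailed row. This follows from the text alone. For a blank period, the SAP leaves open whether blank counts as 'unknown'; if it does not, the result is again 'no'.

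The number of patients concerned is unknown and may be small or nil. The 0.8% to 4.1% of the 'no' group, and the loss of 0.1 to 0.4 points from a 10-point difference, rest entirely on the assumed smoking share, pattern share and reaction rates. The wider scenarios lose at most 1.2 points. The reach is limited to the smoking rows of Table 1.12, the exploratory tests in 2.9, 3.4 and 3.4.1, and a 2.9.xx table if smoking history is significant in 2.9. Overall incidence and remission results are not touched.

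**What to change.** Reword the presence/absence row in SAP 10.1 as follows:

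- Class the patient as 'with smoking history' whenever the positive answer, 'smoking' or 'in the past' is ticked, or any entry is made in either smoking period.
- Keep the existing 'unknown' and 'not provided' rules for the remaining forms.
- State which takes precedence when 'unknown' is ticked and a period is also written. The present rows disagree there too: the first gives 'unknown', the second a smoker.
- Assign 'no smoking history' only to forms that meet none of these.

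This covers the blank-period case without having to decide whether blank means 'unknown'. It does not depend on a separate box for a negative answer, which neither row mentions.

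The cost is a short change to one row of the SAP and the matching derivation code. A cross-tabulation of the two smoking variables in the locked data would show whether any form is affected: a 'no' paired with 'smoking' or 'only in the past' is the direct conflict, and a 'no' paired with a detailed 'unknown' points to the blank-period case.

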	concomitant medication.
	When concomitant-medication data are contained in the survey form,
	it should be classified as "with concomitant medications". When
	there is no description of "presence/absence of prior/concomitant
Presence/absence of	medications" in the survey form or the assessment is impossible, it
concomitant medication	should be classified as "unknown/not provided", and other cases are
	"without concomitant medications".
	◆ Data with drug names in "the administration status of
	prior/concomitant medications for colitis ulcerative", "the
	administration status of other concomitant medication" of the survey
	form.

Data name	Derivation and calculation methods
Data name	 Derivation and calculation methods When the year and month are described for the first administration date of the concomitant medication, impute "1" for the "date". When the year is described for the first administration date of the concomitant medication, impute "1" each for the "month" and "date". When the year and month are described for the final administration date of the concomitant medication, impute the month's final date for the date. When the year is described for the final administration date of the concomitant medication, impute "12" for the month and "31" for the date. When the final administration of concomitant medication < the first administration date of Humira, and/or when the final administration date of Humira < the first administration date of concomitant medication. If the above imputing methods do not help add the date (the first administration date or the final administration date is not provided, etc.), or if the first administration date of concomitant medication are reversed, it should be regarded as a
	 Data with drug names in "priortreatment history for colitis ulcerative" of the survey form When the year and month are described for the first administration date of the prior medication, impute "1" for the "date". When the year is described for the final administration date of the prior medication, impute "1" each for the month and the date. If the final administration date of the prior medication ≥ the first administration date of Humira, regard it as a concomitant medication. If the above imputing methods do not help add the date, the final administration date of the prior medication shall be unknown and the case should not be regarded as a concomitant medication.

Data name	Derivation and calculation methods

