Presence/absence of concomitant medication (6-mercaptopurine) Presence/absence of concomitant medication	Refer to "171218 drug list_UC". If concomitant-medication data of the applicable drug code are provided in the survey form, regard the case as "with 6-mercaptopurine". Others are "without 6-mercaptopurine". Refer to "171218 drug list_UC". If concomitant-medication data of the applicable drug code are provided in the survey form, regard the
(azathioprine &	case as "with azathioprine & 6-mercaptopurine". Others are "without
6-mercaptopurine) Presence/absence of concomitant medication (tacrolimus & ciclosporin)	azathioprine & 6-mercaptopurine". Refer to "171218 drug list_UC". If concomitant-medication data of the applicable drug code are provided in the survey form, regard the case as "with tacrolimus & ciclosporin". Others are "without tacrolimus & ciclosporin".
Presence/absence of	Refer to "171218 drug list UC". If concomitant-medication data of
concomitant medication (antibiotics)	the applicable drug code are provided in the survey form, regard the case as "with antibiotics". Others are "without antibiotics".
Presence/absence of concomitant medication (others)	When concomitant-medication data on the drug code applicable to the drug other than aminosalicylic acid drug, corticosteroids, azathioprine, 6-mercaptopurine, tacrolimus, ciclosporin and antibiotics are included in reference to "171218 drug list_UC", regard it as "with others". Other cases are "without others".
Presence/absence of administration of anti-hepatitis B virus agent	If the following drug codes are included in the survey form, regard the case as "with administration of an anti-hepatitis B virus agent". Others are "without administration of an anti-hepatitis B virus agent". Entecavir (Baraclude): 6250029 Tenofovir (Tenozet, Viread): 6250024 Adefovir (Hepsera): 6250026 Lamivudine: 6250006, 6250020
Presence/absence of concomitant therapy	It should be described in "non-medicinal treatment/concomitant therapy (including surgery) for colitis ulcerative" of the survey form. The data from the first administration date to the final administration date of Humira will be calculated. Such data are also subject to calculation even if the first/final administration dates of concomitant treatment are not unknown. (Only when the days are not overlapped with the administration

Data name	Derivation and calculation methods
	period of Humira, they shall be excluded from the calculation.) When

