Detailed classification of "with" biological products	Infliximab, other biological products Reason for discontinuation: lack of effectiveness Reason for discontinuation: adverse events Reason for discontinuation: others Reason for discontinuation: unknown/not provided
Concomitant medications for colitis ulcerative Details classification of	Without the history, with the history, unknown/not provided
Details classification of	Aminosalicylic acid products, corticosteroid, azathioprine &

Data	How to stratify
concomitant	6-mercaptopurine, tacrolimus & ciclosporin, antibiotics, others
medications for colitis	
ulcerative	
Concomitant therapy	Without the history, with the history, unknown/not provided
for colitis ulcerative	without the history, with the history, unknown/hot provided
Details classification of	Leukocytapheresis, surgery, enteral nutrition therapy, intravenous
concomitant therapy for	nutrition therapy, others
colitis ulcerative	nutrition dicrapy, outers
Site of disease	Rectum, colon, unknown/not provided
Details classification of	
a site of disease	Sigmoid, descending, transverse, ascending
"colon"	
Site of disease by type	Rectal only (no colon), including any of transverse or ascending site,
Site of disease by type	others, unknown/not provided
Self administration	Without the history, with the history, unknown/not provided
Self-administration	Without the history, with the history, unknown/not provided
error	without the history, with the history, unknown/hot provided
General improvement	Effective or better, ineffective
rate	Effective of better, memective
Detailed classification	
of effective or better of	Markedly effective, effective
general improvement	iviairodiy ciicciive, ciicciive
rate	
Partial Mayo score	\geq 0 and \leq 3, \geq 3 and \leq 6, \geq 6 and \leq 9, unknown/not provided
CRP	$<0.3 mg/dL, \ge 0.3 mg/dL$ and $<1 mg/dL, \ge 1 mg/dL$, unknown/not provided
Endoscopy results	normal or remission mucosa, mild, moderate, severe

12. Handling of data for test/assessment periods

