Sex, pregnancy/nursing, race, age (year), body weight (kg), BMI (kg/m²), duration of illness (year), indication (registration form), allergy history, smoking history, detailed classification of smoking history, tuberculosis test, hepatitis B test, complication, detailed classification of complications, complication/others, medical history, detailed classification of medical history, prior medication for colitis ulcerative, detailed classification of prior medication for colitis ulcerative, treatment for colitis ulcerative, detailed classification of medical product, concomitant medication for colitis ulcerative, detailed classification of "with" biological product, concomitant medication for colitis ulcerative, detailed classification of concomitant medication for colitis ulcerative, concomitant treatment for colitis ulcerative, detailed classification of the disease site "colon", site of disease by type, partial Mayo score, CRP

Note: For the discontinuation reasons for the detailed classification of pregnant/nursing or 'using' biological products", calculate the percentage to the aggregation item right above the item. For other items, calculate the percentage to the number of target patients.

Overlapped aggregation may occur in the detailed classification of complications and complication of other classification, detailed classification of medical history, detailed classification of prior medications for colitis ulcerative, detailed classification of prior treatment for colitis ulcerative, detailed classification of 'using' biological products', detailed classification of concomitant medications for colitis ulcerative, detailed classification of concomitant treatment for colitis ulcerative, and the detailed classification of site of disease for colitis ulcerative and the site of

disease "colon".

"1.13 Incidence of self-administration error"

Patients for analysis: patients in the safety analysis group

Analysis objective: to show the distribution status for presence/absence of self-administration and the detailed classification of self-administration.

Analysis item: calculate the number of patients in the analysis groups.

Calculate the number of patients per "self-administration" defined in "11. How to stratify data" and the percentage to the number of patients in the analysis groups.

In addition, calculate the number of patients per "self-administration error" and the percentage to the patients 'with' self-administration.

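### Thirteen of the 57 factors tested in SAP Tables 2.9, 3.4 and 3.4.1 are classified by any use during treatment, so self-administration, and treatments started because of the outcome, can show associations where there is no effect

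*SAP*

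**What the plan says.** **Factors.** Table 2.9 (SAP 13.2) lists 57 patient background factors. Table 3.4 (SAP 13.3) repeats the list and Table 3.4.1 refers to it. All three use Fisher's exact or Mann-Whitney tests, one factor at a time, at two-sided 5% (SAP 9.6). Factors significant in 2.9 each receive a further descriptive table (2.9.xx).

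**Classification (SAP 10.1).**
- Self-administration: if the "column is checked at least once, the case should be classified as" exposed. All others are unexposed, and there is no time window.
- Concomitant drugs: any overlap with the Humira period counts. A drug taken before Humira is included if it continues: "If the final administration date of the prior medication ≥ the first administration date of Humira, regard it as a concomitant medication". The condition "when the final administration date of Humira < the first administration date of concomitant medication" describes drugs begun after the last dose. I read these as left out, because the parallel rule for anti-tuberculosis drugs says so. A start known only to the month is set to the 1st ("When the year and month are described for the first administration date of the concomitant medication, impute" the first day), and a drug whose dates cannot be completed counts as concomitant.
- Concomitant therapies, including surgery: "The data from the first administration date to the final administration date of Humira will be calculated".

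**Outcomes.** In discontinued patients, reactions count up to 28 days after the last dose; in the others, up to Day 1 + 392 (SAP 2). General improvement is judged at Week 52 or at discontinuation (Table 3.4). Remission is taken at the final assessment (Table 3.4.1).

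**The concern.** Time on drug acts on both sides of each comparison. A patient who stops in week 3, before learning to self-inject, is filed as not self-administering, has a short window for reactions, and is scored for effectiveness at an early and probably unsuccessful stop. A patient who stays a year has many chances to be ticked once. That is immortal time. Separately, no rule requires a drug or therapy to begin before the reaction or the failing response, so a steroid course or an operation prompted by the outcome is tested as though it might explain the outcome.

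Factors affecting safety and efficacy are purpose 3 of the survey (Protocol 1, SAP 4.1), and safety by self-administration is a named analysis item (Protocol 9, SAP 5.1). The three tables do not separate use at Day 1 from later use, so a reader cannot readily tell a candidate factor from a by-product of time on drug. A larger sample makes such a signal stronger.

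**Working it through.** **1. Count.** Self-administration 1 + concomitant medication 7 + concomitant treatment 5 = 13 of 57.

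**2. Inputs from the documents.** 1500 patients and 70% dropout (Protocol 2, SAP 4.3), two-sided 5%, Fisher's test, and the windows above. The plan's own figure reproduces: 1500 × 0.30 = 450; 450 × 0.70 = 315; 1.96 × √(0.3 × 0.7 / 315) = 5.1 points. The plan gives no figure for the factor tests. Every other rate below is an assumption.

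**3. Effectiveness against self-administration, no true effect.** Assume that 60% would self-inject, with a start unrelated to outcome, and that treatment is effective in 80% of completers and 30% of those who stop. 70% drop out.

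| Self-injection starts (days) | Exposed | Effective, exposed vs not | p<0.05 |
|---|---|---|---|
| 0-28 | 57% | 45.7% vs 43.9% | 11% |
| 14-84 | 50% | 47.7% vs 41.9% | 61% |
| 28-168 | 43% | 51.1% vs 40.4% | 99% |

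Check of the last row: effective share = 30% + 50% × completer share. The completer shares are therefore (51.1 − 30)/50 = 42.2% in the exposed and (40.4 − 30)/50 = 20.8% in the others. Weighted, 0.43 × 42.2 + 0.57 × 20.8 = 30.0%, which is the 30% who complete. The whole gap is a difference in completer mix. Pooled rate 45.0%; SE = √(0.45 × 0.55 × (1/645 + 1/855)) = 2.6 points; 10.7/2.6 = 4.1 SE. In the first row the gap is 1.8/2.6 = 0.7 SE.

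**4. Reactions against self-administration, no true effect.** Assume a reaction hazard of 0.30 per year, non-responders stopping at twice the hazard of responders, 30% never self-injecting, and the rest starting after week 4 with a mean delay of 16 weeks.

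| Dropout | Reactions that stop Humira | Reactions, exposed vs not | p<0.05 |
|---|---|---|---|
| 70% | none | 21.8% vs 13.0% | 98% |
| 70% | half | 18.8% vs 16.9% | 15% |
| 40% | half | 22.0% vs 25.4% | 29% |

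Repeat runs of the first row gave 21.2-21.5% vs 12.5%. The third row has the opposite sign: a reaction that ends treatment also prevents later self-injection.

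Over 18 scenarios at 70% dropout (0, 30 or 50% never; 0, 50 or 80% of the rest starting at dose 1 or 2; none or half of reactions stopping Humira), rejection was 4-100% in 2.9, 12-100% in 3.4 (50% effective), and in 3.4.1 9-100% with 30% remission or 6-99% with 14% (0.8 × 10% + 0.2 × 30%, the rates in Protocol 2). If response does not affect stopping, 3.4 and 3.4.1 fall to 4-7%. In a repeat run with 80% early starts, 2.9 fell to 5-26%.

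**5. Concomitant treatment, no true effect, 70% dropout, 60% on the drug at Day 1.**
- Later starts at random: 5-7%.
- Started for 20% of reactions, with none / half / all reactions stopping Humira: 55 / 15 / 5% in 2.9. The last figure shows the exclusion of drugs begun after the last dose at work.
- Started in 20% of non-responders, with all / half / a quarter of starts inside the Humira period: 87 / 34 / 11% in 3.4 and 81 / 32 / 11% in 3.4.1 (30% remission).
- Extreme case with nobody on the treatment at Day 1, 30% per year starting at random, and the response model of step 3: 98% for effectiveness.

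**6. Surgery as a factor in 3.4.** With 750 ineffective patients and all operations among them, 5 operations give p of about 2 × 0.5⁵ = 0.06 and 6 give about 2 × 0.5⁶ = 0.03. Surgery in 1% of them is 7.5 operations, close to that threshold; in 2% it is 15, well past it.

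**7. The remedies under no effect.** A Day-57 landmark for self-administration rejects in 3-9% of runs, and Day-1 drug status in 3-6%.

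**The case against.** The strongest defence has four parts.

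- **It is an exploratory screen** in a single-arm survey, and significance in 2.9 leads only to descriptive tables. That limits the consequence. It does not cure a rule that can produce systematic rather than chance associations for a stated purpose and a named analysis item.
- **Each of the 12 concomitant factors has a prior-medication or prior-treatment counterpart** in the same tables, collected for the 3 months before Humira (Protocol 8). This stands as a partial answer: those rows are not Day-1 status, but on-treatment use does not define them. Self-administration has no counterpart.
- **Many concomitant drugs will be ongoing at Day 1**, since the survey enrols patients whose existing treatment was ineffective (Protocol 3). This also stands: such factors are about nominal unless later starts are driven by the outcome. Leaving out treatment begun after the last dose limits this further, although the month-only rule can move a start back to before that dose.
- **The size rests on undocumented rates.** True; rejection for reactions can be nominal and the sign can reverse.

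A reader might infer that all 13 rows are biased, that any significant one is false, or that the direction is known. The documents support none of these: they give no uptake timing, no rate of new starts, and no share of reactions that end treatment.

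**Conclusion.** The point holds in a limited form. Thirteen of 57 tested factors are defined after baseline while outcome observation follows time on drug. Self-administration is the clearest case, because it needs no outcome-driven start. SAP 10.1 has the form ask for a reason when dose 1 or 2 is self-administered, which suggests that routine self-injection begins later, where the distortion is larger. Treatments started for a reaction or for non-response are also exposed; drugs mostly in use at Day 1 are about nominal.

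With 1500 patients and 70% dropout, false-positive rates for self-administration run from about nominal to nearly 100%. The effectiveness tables are affected only if response influences stopping. These are ranges over assumptions and do not predict this survey's results. The change is worth making because it is cheap.

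**What to change.** 1. In 2.9, 3.4 and 3.4.1 show the 13 factors descriptively, labelled as post-baseline, any use during treatment. Omit their p-values, so that they do not trigger 2.9.xx.
2. For self-administration add a landmark comparison, for example at Day 57, in patients still on drug (and reaction-free for 2.9), counting later outcomes only. Table 3.1.7.1 already conditions on Week 8. Place it beside Table 2.5, and label 2.5 as ever/never during treatment.
3. For concomitant drugs only, test use ongoing at Day 1, as Table 3.6 does for steroids. Set to unknown any record whose start relative to Day 1 is undated or rests on an imputed date.
4. For surgery and other episodic therapies, rely on the existing prior-treatment factors as the tested baseline version. In the effectiveness tables report on-treatment surgery as an outcome.

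Two apparent shortcuts should be avoided. Self-administration status at dose 1 or 2 may have few exposed patients, given the reason the form asks for, and surgery on Day 1 would be nearly empty.

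**Cost.** SAP wording and reprogramming; no new data, since the method of administration is recorded at dose 1, dose 2 and later (Protocol 8). Precision falls: the simulated landmark had 130 to 1019 exposed patients at 70% dropout. It omits early stoppers and early reactions, 20-22% of patients at 70% dropout and 10-12% at 40%. Records set to unknown leave the tests (SAP 9.2, 9.5). Day-1 status dilutes a real effect of later starts: if a drug doubled the reaction hazard and 6-24% of Day-1 non-users started it later, a 13.2-point difference would shrink to 12.6-10.8 points.
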